Recruitment of CAB: Sampling will be purposive. The CAB will consist of 5 older adults who have finished cancer treatment with chemotherapy within the past 3 years, 3 family caregivers, and 2 oncology staff nurses who deliver chemotherapy treatments. Older adults and caregivers are the critical voice of the target audience, and oncology trained nurses are important to verify accuracy of recommended CINV self-management strategies within the game and current treatment center discharge instructions. To the greatest extent possible, all CAB members will be present at each focus group. CAB members will provide input for scenarios (incidence, self-management, perceived and actual consequences) based on their experiences with CINV. Older adults will be recruited from a pool of approximately 109 participants from the PIs prior research studies who agreed to be contacted for further research.

Names will be randomly drawn from this pool; an invitation to participate will be mailed in batches of 10

Figure 3: Principles of Serious Gaming

- Knowledge sets stage for behavioral change
- Practicing skills leads to self-mastery
- Modeling is an effective way to learn new skills
- Tailored games facilitate character identification
- Game must be entertaining

until target numbers are reached. Nurses will be recruited from the UF Health Cancer Center-Orlando chemotherapy treatment center. Retention will be enhanced by offering a \$50 stipend/gift card to the CAB members for each focus group they participate in. Informed consent and participant characteristics (e.g., age, gender, race, educational level, CINV experience) information will be collected from all CAB members.

Phase II - Game prototype testing

Phase II will use a prospective 2-group randomized, longitudinal design to evaluate effect size of the intervention, examine group differences and evaluate game appeal. Patients who meet the inclusion criteria will be randomly assigned into the intervention group or control group at a 1:1 ratio. All participants will be followed for four chemotherapy cycles (approximately 4 months).

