Setting: The outpatient treatment center at the UF Health Cancer Center-Orlando will be the primary site for enrollment due to its long-standing relationship with these researchers. In 2013, UF Health Cancer Center-Orlando saw approximately 4,694 patients. Of these 2,573 patients were age 65 or older, and 565 of these patients received outpatient chemotherapy. These numbers indicate an ample sampling pool of older adults.

Sample size: The target sample is older adults receiving emetogenic chemotherapy for the first time. Sixty-six participants will be enrolled if they meet the following **inclusion criteria**: age 65 and older, newly diagnosed with any cancer, treatment with any chemotherapeutic agent with a moderate to severe emetic potential (on a 3- or 4- week cycle), proficient in English, and have a telephone. **Exclusion criteria** include: previous diagnosis and treatment for cancer, advanced or end stage disease with a palliative intent, visually or hearing impaired. Dementia or cognitive impairment is not a concern with the population since they have already been cognitively screened in order to consent to treatment at this cancer center. There will be no exclusion based on gender or racial/ethnic status. Retention of all participants will be enhanced by the following strategies 1) weekly telephone follow-up phone calls by the RA; 2) a \$50 incentive/gift card at the end of the study period; and 3) attention control group offered eSSET-CINV at the end of the study. We will oversample by 20% in order to account for attrition.

Phase II Procedures:

Recruitment and randomization: Successful recruitment and retention strategies previously established by the team will be used during this phase.^{7, 15, 16, 18, 90} Convenience sampling, followed by randomization will be used. All new patients will be screened for eligibility by the Research Nurse (RN-PG) using the Sunrise XA -

electronic medical record system used by Orlando Health. Eligible patients will be approached by the RN at their first chemotherapy appointment and asked to participate. This timing is not expected to add to or create patient anxiety. Patients usually wait 30 to 60 minutes for lab results and chemotherapy to be delivered. Participating

Table 1: Intervention schema

	Pre-treatment		First Treatment Visit			Post - treatment

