	Standard written patient education at admission to cancer center	Standard written patient education at treatment planning visit	ENROLL/ RANDOMIZE	eSSET-CINV Intervention: 1) Game 2) Decision discussion with research nurse	Standard review of written patient education on side effects	Follow-up phone call
All subjects	x	x	IG	x	x	x
			ACG		x	x

Note: IG= Intervention Group, ACG=Attention Control Group

may act as a distraction, thus reducing anxiety. In addition, patients have already received standard written education regarding treatment effects and will expect CINV as a possible effect of treatment. Written informed consent will be obtained in a private area of the clinic open to the RN. A signed copy of the consent will be given to the patient. Once informed consent is obtained, baseline measures will be completed, and participants will be randomized (Intervention Group [IG] and Attention Control Group [ACG]) to either group by choosing an envelope with a group assignment.

Participants in each group will receive **standard care**: 1) *on admission* to the cancer center (receipt of standard written educational materials that patients are instructed to bring to each appointment), 2) *at a treatment planning visit* (receipt of specific handouts regarding treatment and potential side effects, and 3) *at time of treatment* (verbal review of chemotherapy and symptom handouts by treatment center nurses). See Table 1 for an outline of standard education and eSSET-CINV intervention.

Study Variables

Independent variable: Intervention versus Attention Control group

1) Intervention Group

The intervention will consist of two parts: 1) the eSSET-CINV game and 2) decision discussion with research nurse (RN). The game will be administered by the RN. Participants will play the game at the outpatient treatment center prior to their first chemotherapy treatment using either a study-provided laptop or smart tablet using headphones to ensure privacy and limit distraction. Please see Table 2 for the eSSET-CINV intervention process. At the end of game play, the RN will engage the participant in a discussion about the self-management choices the player made and suggest changes or discuss possible outcomes based on different choices. For example, if the player chose not to treat the avatar's mild nausea and vomiting occurred, the RN would discuss more effective self-management choices as outlined in Figure 3.

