The players will be allowed to play the game as many times as they choose during that chemotherapy visit in order to practice making decisions and visualizing consequences and outcomes. Once the participant is discharged home, a student RA, blinded to the treatment group, will call participants weekly to see how they are doing and remind them to record self-management data. To reduce bias, a scripted interview form will be used. Student RAs will instruct the participant to follow cancer center procedures and call their oncologist if they are having problems or have questions.

Intervention fidelity. eSSET-CINV will be presented and delivered by the same RN each time. The RN will base the discussion on common self-management options (Figure 3). Minor interruptions (< 10 minutes) to game play will be recorded and participants will resume game play where they left off. Technology malfunctions (e.g., system crash or frozen screen) will be recorded and participants will be asked to start eSSET-CINV over. For players with caregivers, caregiver involvement (e.g., helping, prompting) in the game will be recorded for subgroup analysis.

2) Attention Control Group

Participants in the control group will receive: 1) standard care; 2) follow-up phone calls from the student RAs to remind them to record self-management data; and 3) the opportunity to play eSSET:CINV at the end of the study period. During the follow-up phone calls, the student RAs will instruct the participant to follow cancer center procedures and call their oncologist if they are having problems or have questions. Contamination between groups is not expected since participants are likely scheduled for chemotherapy at different times and receiving treatment in different areas of the treatment center.

Co-variates

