The one-way repeated measures ANOVA will be used to assess the difference between the two groups. The mixed effect model may be used as exploratory analysis to account for unobservable variations from each individual patient. In addition, comparisons between two groups at each treatment cycle time point will be performed for all primary and secondary endpoints. For this particular comparison, the univariate normality of each endpoint will be assessed graphically at each treatment cycle time point. An appropriate time window will be determined to define the treatment cycles for the study.

AIM 3: Obtain preliminary data regarding the feasibility and acceptability of the game in older adults experiencing CINV. Feasibility- Computer science and digital media undergraduate students will work under the direction of [name] and [name] to identify patterns in game play data (e.g., self-management decisions, scenario patterns of progression), time to game completion, and number of times the game was played (intervention dose). The RN will track any instance of game play interruptions or

malfuction. This data will be summarized with descriptive statistics. **Game Appeal:** Responses to the game appeal and willingness to recommend questions will be scored and summed using descriptive statistics. Additional comments about the game will be recorded and analyzed for themes.

Sample size and statistical power:

Based on the assumption of a nausea severity mean score of 6.20, range from 2 to 9, a standard deviation of 2.44, and a clinically meaningful difference in mean nausea severity score of one between the intervention and control groups, with 90% power, the required sample size is 33 participants for each group, yielding a total sample size of 66 for the study. To reduce the patient selection bias, single-blinded randomization may be used whenever feasible. Due to lack of available data from prior research the sample size for secondary endpoints is not possible for the study at first stage. However, the power statistical analysis will be assessed when data become available from the planned study.

Potential challenges and strategies for addressing:

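### Having each participant pick an envelope, with no fixed order or safeguards described, does not secure allocation concealment, and conditional single-blinding is not a remedy for selection bias

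*Combined protocol and SAP*

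**What the plan says.** The Phase II design paragraph states that eligible patients will be "randomly assigned into the intervention group or control group at a 1:1 ratio". The mechanism is in Phase II Procedures, Recruitment and randomization: "Once informed consent is obtained, baseline measures will be completed, and participants will be randomized" "to either group by choosing an envelope with a group assignment". The text available says nothing more about who makes the sequence, how the envelopes are prepared or kept, or whether blocks or strata are used.

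On staffing, the same section says "All new patients will be screened for eligibility by the Research Nurse" and "Eligible patients will be approached by the RN at their first chemotherapy appointment and asked to participate". Under Intervention fidelity, "eSSET-CINV will be presented and delivered by the same RN each time". Sampling is by convenience.

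The only statement about selection bias is in Sample size and statistical power: "To reduce the patient selection bias, single-blinded randomization may be used whenever feasible".

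Moderate and severe emetic potential are both eligible. The Co-variates section records the chemotherapy regimen and antiemetics at baseline, among characteristics that may affect CINV. The Data Analysis section does not name either as an adjustment variable.

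**The concern.** Concealment means that whoever decides to approach or enrol a patient cannot know or influence the next assignment. A free pick from a set of envelopes leaves two gaps. First, there is no pre-set order against which an allocation can be checked, so nothing would show whether an envelope was put back and another taken. Second, the nurse role that recruits also delivers the game, and so knows who received it and, by elimination, who did not. With convenience sampling, that knowledge could affect who is approached and when.

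Blinding does not answer this. It limits how people behave or report once an assignment has been made, whereas selection bias enters before that. The plan's sentence is also conditional and does not say who would be blinded.

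At stake is the comparability of the arms in a trial of 66. Both primary endpoints, nausea and vomiting severity and the number of self-management behaviors, are self-reported by patients who know whether they played the game. Any difference in who enters each arm would look like a treatment effect.

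**Working it through.** The plan gives no figure for concealment or balance that could be reproduced. The inputs it does give are 33 per group (66 in total), SD 2.44, a target difference of 1 point and a 20% oversample. Whether 33 per group is enough is a separate question; it is taken as given here.

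**Step 1. Two readings of the envelope rule.** They have different consequences and cannot both hold.

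- *Independent draws.* The number in one arm is Binomial(66, 0.5). P(exactly 33/33) = 0.098. P(arm sizes differ by 10 or more) = 0.268. The central 95% range for one arm is 25 to 41. A 25/41 split keeps 4 × 25 × 41 / 66² = 4100/4356 = 94% of the information of an equal split. Past results do not help to predict the next one.
- *A fixed deck of 33 + 33, used up.* Final balance is exact, but late picks become predictable. Suppose someone remembers every assignment and always guesses the arm with fewer patients so far, tossing a coin at ties. By simulation, that person makes about 4.6 more correct guesses than the 33 expected by chance, and on average about the last 2 picks are certain.

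**Step 2. Would small blocks help?** The same guessing rule was applied to permuted blocks of 4 and 6 in two strata. It gives about 12.2 excess correct guesses, and 12.2/4.6 is roughly 2.6 times the fixed-deck figure. Block size drives this; without strata the count is about the same. In a trial where one nurse sees the assignments, small blocks buy balance at the price of predictability.

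**Step 3. Chance imbalance on emetic potential.** The share on severe-risk regimens is not given; 20% to 50% is assumed. With N = 66:

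| Gap between arms in severe-risk share | Fixed 33/33 deck (hypergeometric) | Independent draws (simulation) |
|---|---|---|
| 15 points or more | 18% to 33% | 14% to 27% |
| 20 points or more | 6% to 14% | 5% to 11% |

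If severe and moderate regimens differ by 2 nausea points (assumed; range 1 to 3), a 20-point gap shifts the observed difference by 0.20 × 2 = 0.4 (0.2 to 0.6), against the target of 1. The standard error of the difference is 2.44 × √(2/33) = 0.60, so 0.4 is 0.4/0.60 = 0.67 standard errors. Under valid randomization this is part of ordinary sampling error, not bias.

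**Step 4. Envelopes needed.** 66 × 1.2 = 79.2, so 80; or 66 / 0.8 = 82.5, so 83.

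**The case against.** The strongest reply is that the protocol already has the most important ordering right. Consent and baseline measures come before the envelope, so the patient is enrolled and measured before any assignment is drawn. The weekly callers are blinded and use a scripted form. Both are real safeguards and should be credited. Neither hides upcoming assignments from the person choosing whom to approach, and neither shows that the first pick stood.

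Several stronger readings are tempting, and the documents do not support them:

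- *That the nurse takes consent, holds the envelopes and watches the choice.* The text says only that consent takes place in an area open to the nurse. It names no custodian and does not say who is present. Nor does this nurse give the chemotherapy; the role delivers the game and the discussion.
- *That 1:1 balance fails.* This holds only with independent draws, and then the power cost is small. With a fully used deck, balance is exact. Predictable late picks and unequal arms cannot both be charged against the same procedure.
- *That emetic risk biases the result.* The calculation rests on an assumed share and an assumed effect, and describes chance imbalance.
- *That the trial must stratify in small blocks.* Small blocks would make assignments easier to guess here. Stratification in a trial of this size is a reasonable option, not a requirement.

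A short stretch of the document, before the student-training paragraph that precedes Preliminary Studies, was not available, so further allocation detail there cannot be ruled out.

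**Conclusion.** The point stands as a gap in allocation concealment that should be closed. The stated rule is a free pick with no fixed order, the recruiting role also learns assignments, and the remedy offered against selection bias is the wrong kind of safeguard and is conditional. No one is shown to have influenced allocation, and the resulting bias cannot be sized from the documents.

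The numbers that can be given are secondary. Arms differing by 10 or more in 27% of trials assumes independent draws and costs little power. A 0.2 to 0.6 point shift from a 20-point emetic-risk gap assumes a 1 to 3 point effect; such a gap has a 5% to 14% chance if 20% to 50% of patients are on severe-risk regimens. Adjusting for emetic potential is worthwhile because it uses information already collected, not because leaving it out makes the comparison invalid.

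**What to change.** 1. In Recruitment and randomization, replace the free pick with sequentially numbered, opaque, sealed envelopes. A team member with no patient contact prepares them from a computer-generated 1:1 list. They are opened strictly in order, after baseline measures, and each opening is logged with envelope number, participant, date and time. Prepare enough for the oversample (80 to 83), with spares in each set if strata are used.
2. In Sample size and statistical power, replace the single-blinding sentence with this concealment statement. If blinding is kept, describe it separately and say who is blinded.
3. Name emetic potential (moderate or severe), classified from the regimen recorded at baseline, as a covariate in the longitudinal between-group model.
4. State whether the list is restricted. If so, use large or varied blocks whose sizes are not disclosed to site staff. Stratification by emetic potential is optional.

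If enrolment has already taken place, document the procedure actually used and apply item 3.

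The cost is a list, the envelopes, a log and a few sentences of protocol text, some time from a person without patient contact, and one extra term in the model. No new data are needed.

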Nursing students will be an integral part of the team and will be active research assistants (RAs) throughout this study. All students will receive training in research and will be required to undergo CITI training as required by the UCF Institutional Review Board. All students will be educated on cancer chemotherapy side effects and self-management behaviors prior to working with research subjects. In phase I, students will be trained to participate in focus groups (e.g., note taking), analyze focus group data (e.g., review transcripts, code, and develop themes), and pre-test the eSETT:CINV game. In phase II, students will be trained in the following: 1) data base setup, data entry, and cleaning; 2) conduct follow-up phone calls and data collection; and 3) develop a questionnaire to elicit feedback about the games appeal and usability. Pre-nursing students, undergraduate Honors in the Major students, and graduate students have a strong record of research within our college with many students conducting their own research or working on faculty projects. Students engaged in this project will be exposed to cutting-edge technology and patient education and have opportunities to publish and present their work related to this project at university, local, and regional research conferences. This project will provide a research foundation that they can use for their own research careers.

Preliminary Studies:

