of self-management strategies used and, 3) the strategies *perceived helpfulness* in reducing nausea (0-10 Likert scale). Preventative self-management activities for CINV will also be recorded. All self-management strategies are coded (e.g., “MED”= taking antiemetic, “DIS”- using distraction), and the participants will fill in the strategy code they are using on the form. To lessen the risk of the SMC becoming an intervention for the Control Group, all participants will be asked to record self-management behaviors of other common treatment-related symptoms (i.e. fatigue, mouth/throat sores). The SMC will be collected by the research nurse at chemotherapy cycles 2, 3 and 4.

4) Health-related Quality of Life- The EORTC-30⁹² will measure QOL at each treatment cycle. This frequency is consistent with others studies that have measured QOL in older adults over time.^{59, 93} This well-known scale includes 5 functional scales, 3 symptom scales, and 6 single items using a 4-point Likert scale (“not at all” to “very much”), and 2 global health/QOL items using a 7-point Likert scale (“very poor” to “excellent”). Higher scores on the functional and health/QOL scale indicate better functioning, while higher scores on the symptom-related scales and items indicate higher symptoms. Reliabilities (Cronbach's alphas) range from 0.52 (role functioning scale) to 0.89 (QOL).⁹²

5) Resource Use: Any unplanned Emergency Department or hospital admission will be recorded via participant report using a dichotomous (Y/N) variable at each follow-up phone contact and treatment visit. Follow-up questions about the reason for the admission, length of time for admission and treatment will also be asked. The report will be verified by medical record review whenever possible.

Additional Outcomes:

Game appeal: Under the guidance of the PI, student RAs will develop and pre-test a short survey to evaluate game appeal at the first follow-up phone call. Using a 4-point agreement scale, participants will be asked the extent to which they agree or disagree with statements regarding ease of game play, game likability, clarity of self-management choices, usefulness in educating about CINV consequences and ability to be controlled/cured, and realism (setting and scenario). Additional comments about the game will be recorded.

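### The weekly caller is said to be blinded, but a survey that only game players can answer is set for the first call, and no other person is named to give it

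*Combined protocol and SAP*

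**What the plan says.** Under Study Variables, 1) Intervention Group, the protocol states that after discharge "a student RA, blinded to the treatment group, will call participants weekly to see how they are doing" and adds "To reduce bias, a scripted interview form will be used". The Attention Control Group also receives its follow-up calls from the student RAs. Its access to the game is limited to "the opportunity to play eSSET:CINV at the end of the study period". Intervention participants play before their first chemotherapy, so before any call.

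Under Additional Outcomes, Game appeal, "student RAs will develop and pre-test a short survey to evaluate game appeal at the first follow-up phone call". The items ask about ease of play, likability, clarity of choices, usefulness and realism. The sentence on asking participants is in the passive and does not say who asks.

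The paragraph on student roles that precedes Preliminary Studies gives students both tasks: "conduct follow-up phone calls and data collection; and 3) develop a questionnaire to elicit feedback about the games appeal and usability". The same list includes "data base setup, data entry, and cleaning".

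Under Dependent Variables, 5) Resource Use, any unplanned ED or hospital admission is asked about at every phone contact and every treatment visit, with follow-up questions and a record check where possible. The section headed Principle data analysis makes admissions a secondary endpoint and the number of self-management behaviors a primary one. The only other blinding statement, under Sample size and statistical power, is "To reduce the patient selection bias, single-blinded randomization may be used whenever feasible". It does not say who is blind.

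**The concern.** The caller is the only person whom the available text names as blinded. The apparent purpose is to keep the caller's probing, follow-up questions and encouragement the same in both arms. A survey about playing the game, placed in the first of those calls, works against that purpose because at that point only one arm has a game to rate.

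Two things pass through the weekly calls. The first is the admission question with its follow-up on reason, duration and treatment. The second is the reminder to keep recording self-management data. A caller who knows the group could probe for admissions differently, or press one arm harder to complete the checklist. The second route is indirect, but it leads to a primary endpoint. In addition, if the survey was given by the weekly callers, a report that those callers were blinded would be inaccurate.

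**Working it through.** The plan gives no figure to reproduce. The check is whether its statements can all hold at once.

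1. **Who calls.** Student RAs call both arms, and no other caller is described.
2. **Who has played by the first call.** Intervention participants have, before their first treatment. Controls have not, since they are offered the game only when the study period ends.
3. **What can happen at the first call:**
   - The weekly caller puts the survey to everyone. Players rate the game and controls have nothing to rate, so the answers separate the arms.
   - The weekly caller puts it to players only. The caller must then hold a list of players and already knows the group. Omitting the survey marks a control as surely as giving it marks an intervention participant.
   - Someone else gives the survey. Blinding can survive if that person makes no outcome calls to the participant and does not share the information. The text describes no such arrangement.
4. **What follows for later calls.** Knowledge gained at the first call carries forward only if the same student continues with that participant or the students share records. Shared records are plausible, since students also handle data entry. If a different, uninformed student makes the later calls, only the first call is touched. Even there, an admission answer taken before the survey would already be recorded.
5. **What is exposed.** The weekly calls after the first are exposed, through the admission question and the recording reminder. Symptom severity, the self-management checklist and quality of life are completed by participants on paper, and the research nurse collects the checklist. Caller blinding does not protect those measures directly.
6. **A second item of the same kind.** The willingness-to-recommend question, set for Cycle 4 (T4), also names no administrator and presupposes having played.
7. **Recall cost of moving the survey to T2.** Assume the first call comes about one week after the first treatment and there are no cycle delays. Cycles last 3 or 4 weeks, so T2 falls at about week 3 or 4. Added recall is 3 − 1 = 2 weeks to 4 − 1 = 3 weeks.

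**The case against.** The strongest reply is that the conflict rests on silence. The protocol says students develop and pre-test the survey, not that the blinded caller gives it. There is more than one student RA, so a separate one could do it. A stretch of the document just before the student-roles paragraph was also unavailable to this review. This stands as a limit: what is shown is a conflict on the natural reading, not proof that a blinded caller asked the questions. It does not dispose of the point, because the plan states a safeguard and then schedules something that defeats it unless an unnamed second person is assumed.

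A second reply is that the script protects against bias. A script standardises wording, but it does not hide the group, and a section used in one arm only would itself reveal it.

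A third reply is that little depends on caller blinding. Participants know their own group, the admission item is a yes/no question, and reports are checked against records where possible. The item is also asked at treatment visits. The only study person placed there is the research nurse, who knows the group: "eSSET-CINV will be presented and delivered by the same RN each time". All of this stands and keeps the impact modest.

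A reader might go further and infer that this defect compromises the resource-use data at T2, T3 and T4. The documents do not support that. Those time points are treatment visits, no blinded caller is described there, and the nurse's knowledge is a separate matter.

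**Conclusion.** The point holds as an inconsistency that should be corrected. On the natural reading, the game-appeal survey at the first call reveals the group to a caller whom the plan describes as blinded, in both arms. Loss of blinding beyond that call rests on one further assumption: the same caller continues, or the information is shared.

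The impact is modest. It falls on one scripted, self-reported secondary endpoint with partial record verification and, indirectly, on a reminder linked to a primary endpoint. The documents give no basis for estimating the size or direction of any bias. A reader might infer that blinding certainly failed for every participant, or that the admission comparison is biased by some calculable amount. Neither follows: a separate administrator is not excluded, and nothing in the plan measures how callers would behave differently. Correcting the survey would also not make all admission ascertainment blinded, because of the treatment visits.

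**What to change.** Take the game-appeal survey out of the blinded caller's script and name who gives it. There are two workable forms:

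- **A different student RA** from the existing pool, who makes no outcome calls to that participant, gives it at about the time of the first call. This keeps the timing for the acceptability aim.
- **A self-completed paper form**, returned sealed at T2 and opened and entered by someone who does not call that participant. The restriction on entry matters because students also enter data. This costs about 2 to 3 weeks more recall and loses anyone who drops out before T2.

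Handle the T4 willingness-to-recommend item the same way. In either form, keep the list of game players from the callers. If the survey stays with the weekly caller, withdraw the statement that the caller is blinded.

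The change is to protocol and call-script wording and uses existing staff and visits. Participants may still disclose their group unprompted, which no wording change can prevent. If calls have already been made, the report should say who gave the survey and whether the callers were in fact unaware of the group.
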